#### **10.2 Adverse Event Reporting Period**

AEs will be monitored continuously during the study from the time that the subject has provided written informed consent through the subject's last day of study participation. Subjects will be queried and events will be assessed at each clinic visit. A treatment-emergent AE (TEAE) is any AE with an onset from any time from administration of the study treatment through the last study visit, whether or not it is considered causally related to the study treatment.

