#### **10.4 Serious Adverse Event Reporting Period**

All SAEs, whether or not unexpected or considered to be associated with the administration of SB-318, must be reported immediately to Sangamo or its designees by telephone or fax, and must be submitted to Sangamo or its designees on an SAE Report form within 24 hours of the Principal Investigator's discovery of the event. Please refer to the Study Reference Manual for SAE reporting guidelines and contacts.

The reporting period for all SAEs is from subject consenting through the last study visit.

The Principal Investigator is responsible for promptly notifying the IRB/IEC or equivalent in accordance with local regulations of all SAEs. The National Institutes of Health (NIH) requires that all investigators participating in gene transfer research to report all SUSARs. SUSARs will be reported to the appropriate regulatory authorities (FDA/MHRA or equivalent) according to the requirements for expedited safety reporting. Sangamo or its designee will assume the responsibility for reporting SUSARs to the FDA/MHRA or equivalent.

All "serious" events must be followed with appropriate medical management until resolved or stabilized.

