## **12 SUBJECT WITHDRAWAL/DISCONTINUATION, AND SAFETY MONITORING COMMITTEE**

### **12.1 Subject Withdrawal and Discontinuation from Study**

Subjects may withdraw or should be discontinued from study for any of the following reasons:

- Request by the subject to withdraw.
- Request of Sangamo or primary care provider if he or she thinks the study is no longer in the best interest of the subject.
- Pregnancy prior to SB-318 infusion.
- Subject judged by the Principal Investigator to be at significant risk of failing to comply with the provisions of the protocol as to cause harm to self or seriously interfere with the validity of the study results.
- At the discretion of the IRB/IEC or equivalent, Office for Human Research (OHR), regulatory authority (e.g., FDA/MHRA or equivalent), Principal Investigator, or Sangamo.

Subjects will be strongly encouraged to continue and comply with follow-up safety evaluations. If a subject withdraws consent or discontinues from the study post-study treatment, a conference between the Principal Investigator and Medical Monitor will take place to ensure that the subject understands the importance of the study follow-up and that the study treatment cannot be reversed even if a subject drops out of the study follow-up. If the subject agrees, a reduced follow-up testing schedule may be arranged including telephone call and safety labs to assess treatment-related AEs and disease status.

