### **13.4 Primary Endpoint**

The primary endpoint of this study is the incidence of treatment-emergent AEs (including SAEs). Additional safety evaluations will include:

- Routine hematology, chemistry, and liver function laboratory tests, vital signs, physical exam, ECG, ECHO, and concomitant medications.
- Monitoring of chimerism in post-HSCT subjects.
- Cranial nerve exam and muscle strength testing.
- Serial AFP testing and MRI of liver to evaluate for liver mass.

Safety assessment will be performed on all subjects. All reported AEs will be coded to a standard set of terms using the Medical Dictionary for Regulatory Activities (MedDRA).

Treatment-emergent adverse events will be summarized overall and by treatment cohort. For each subject, the maximum reported severity of each adverse event will be used in the summaries by severity grade. In addition, all serious adverse events and AEs related to study treatment will be summarized.

Laboratory data will be summarized for each time-point at which specimens are collected. Change-from-Baseline values may be calculated for selected laboratory parameters. Shift-tables (Change-from-Baseline relative to the normal range) may be constructed for selected laboratory parameters.

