8.1. Primary Endpoint Analysis

8.1.1. Adverse Events

A treatment-emergent adverse event (TEAE) is defined as any adverse event with an onset date on or after the date of the SB-318 infusion through the last study visit, whether or not it is considered causally related to the study drug.

Treatment Emergence:

Totally Missing Dates:

- If both the onset date and the end date are, then the adverse event is assumed to be treatment emergent.

Partially Missing Dates:

- If the onset date is missing and the non-missing end date is prior to the infusion date, then the AE is not considered treatment emergent.
- If the partial end date can be assumed to be prior to the infusion date (month and/or year before infusion date), then the AE is not considered treatment emergent.
- If the end date is after the infusion date or the partial end date can be assumed to be on or after the infusion date (based on month and/or year), then the AE is assumed to be treatment emergent.
- If the onset date is partial and can be assumed to be prior to the infusion date (based on the month and/or year) or the non-missing end date is prior to the infusion date then the AE is not considered treatment emergent.
- If the partial onset date can be assumed to be on or after the infusion date, then the AE is assumed to be treatment emergent.

All AEs will be coded according to the most recent version of the MedDRA. Severity will be categorized by toxicity grade according to the Common Terminology Criteria for Adverse Events (CTCAE) Version 4.03.

AEs not listed in the CTCAE version 4.03 will be evaluated by using the following criteria:

- Grade 1, Mild: Symptoms cause no or minimal interference with usual social and functional activities
- Grade 2, Moderate: Symptoms cause greater than minimal interference with usual social and functional activities
- Grade 3, Severe: Symptoms cause inability to perform usual social and functional activities

- Grade 4, Potentially Life-threatening: Symptoms cause inability to perform basic self-care functions OR medical or operative intervention indicated to prevent permanent impairment, persistent disability, or death
- Grade 5: Outcome of AE is death.

Incidence of Adverse Events

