The incidence of AEs will be summarized in tables with count and percentage of subjects with AEs by system organ class (SOC) and preferred term (PT). Unless otherwise specified, at each level of SOC or preferred term, a subject with multiple events will only be counted once per SOC or preferred term. Percentages of subjects with AEs will be calculated out of the number of subjects in each summary cohort of the intent-to-treat set. Tables will be sorted by SOC alphabetically in overall group and PT in decreasing order on total frequency order.

The following categories of AE will be summarized:

- TEAEs
- Severity (CTCAE Grade 1, 2, 3, 4 and 5) of TEAEs
- TEAEs by relationship to study drug
- Grade 3 or greater TEAEs
- Serious TEAEs
- Grade 3 or greater Serious TEAEs
- Grade 3 or greater TEAE related to study treatment
- TEAEs leading to study discontinuation
- TEAEs leading to death

All AEs will be presented in data listings. TEAEs and SAEs will be flagged in the listings.

Severity of Adverse Events

All AEs will be summarized by maximum severity (CTCAE Grade 1, 2, 3, 4 and 5), SOC, and preferred term. At each level of SOC or preferred term, a subject with multiple events will only be counted once by the maximum severity per SOC or preferred term. No imputation will be done for missing severity. Adverse Events with missing severity will be presented in tables and listings as is.

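### The TEAE window closes at an undefined last study visit while AE monitoring runs to the end of participation, so a reported, fully dated event starting in between is left out of the primary-endpoint tables

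*SAP*

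**What the plan says.** Protocol 10.2 contains two end dates. AEs are monitored "from the time that the subject has provided written informed consent through the subject's last day of study participation". The treatment-emergent subset in the same section is "any AE with an onset from any time from administration of the study treatment through the last study visit". SAP 8.1.1 carries the narrower window into the analysis: "any adverse event with an onset date on or after the date of the SB-318 infusion through the last study visit". Protocol 10.4 gives SAEs the same end: "The reporting period for all SAEs is from subject consenting through the last study visit". Protocol 10.6 also closes its urgent-safety period there.

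Protocol 13.4 and SAP 3.2.1 make TEAE incidence, SAEs included, the primary endpoint. The AE categories listed in SAP 8.1.1 are all restricted to TEAEs, including serious TEAEs, TEAEs causing discontinuation and "TEAEs leading to death". Every AE table shell is likewise titled as a TEAE table. All AEs go into the listings, with TEAEs flagged.

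Three other provisions bear on the point. Protocol 6.10 asks subjects who leave early to attend an Early Termination visit that includes AE assessment. Protocol 10.3 wants the cause of any death recorded as the AE and reported as an SAE. Under Protocol 12.1, if a subject who stops after treatment agrees, "a reduced follow-up testing schedule may be arranged including telephone call and safety labs to assess treatment-related AEs and disease status".

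**The concern.** For a subject who completes the Month 36 visit, the two end dates should coincide. They can separate when a subject dies or is lost between visits. No later visit then exists, so an event that began after the last one lies inside the AE monitoring period but outside the TEAE window. Protocol 10.3 plainly intends a cause of death to be captured, but the SAP's definition would keep it out of the tables that report the primary endpoint.

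The stake is a wrong count and a report that disagrees with itself. Disposition Table 14.1.1.1 counts deaths and adverse events as reasons for early termination with no such window, whereas Table 14.3.3.3 applies it. In addition, an SAE that starts after the last visit falls outside the stated SAE reporting period, so Protocol 10.4 does not assure its collection.

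**Working it through.** The documents give no figure to reproduce. The check is a comparison of windows, plus arithmetic to size the gap.

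**1. End dates side by side.**
- AE monitoring (Protocol 10.2): last day of participation.
- TEAE (Protocol 10.2, SAP 8.1.1): last study visit.
- SAE reporting (Protocol 10.4): last study visit.
- Missing and partial dates (SAP 8.1.1): compared only with the infusion date; no upper limit.

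**2. A test case.** Suppose the last visit is Month 24, about day 730; a fatal event starts on day 765; death is on day 770.
- Window to last visit: 765 > 730, so not a TEAE.
- Window to last day of participation: 765 ≤ 770, so a TEAE.
- Same event with only month and year of onset: the partial-date rule finds it later than infusion and counts it. The better-dated record is the one excluded.

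**3. Which subjects are affected.**
- Completes Month 36: dates coincide; no effect.
- Leaves and attends the Early Termination visit: an earlier event precedes the last visit and counts.
- Dies, but onset preceded the last visit: counts.
- Dies after an onset later than the last visit: not counted.
- Leaves with no Early Termination visit, and an event starting after the last visit is still reported: not counted.

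**4. Length of the exposed interval.** Protocol 6.8 and 6.9 give the visit schedule; a month is taken as 30.4375 days. Maximum gap = nominal gap + the two visit windows.
- Years 2 and 3: 3 × 30.4375 ≈ 91 days; maximum (3 + 1 + 1) × 30.4375 ≈ 152 days.
- Week 52 to Month 15: 15 × 30.4375 − 364 ≈ 93 days; maximum 93 + 7 + 30 = 130 days.
- Week 48 to Week 52: 28 days; maximum 28 + 7 + 7 = 42 days.

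**5. Conditional illustration.** Assume that a subject dies or leaves d days after onset, that onset is uniform within the gap, and that no unscheduled, ERT-withdrawal or Early Termination visit occurs. The chance that no scheduled visit intervenes is 1 − d/gap.
- Gap 91 days: 1 − 7/91 = 92%; 1 − 14/91 = 85%; 1 − 30/91 = 67%.
- Gap 28 days: 1 − 7/28 = 75%; 1 − 14/28 = 50%.
- Gap 14 days (Weeks 2 to 8): 1 − 7/14 = 50%; 1 − 14/14 = 0%.

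These are not event rates, and they do not give the probability that the trial omits an event.

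**6. Effect on one row.** One uncounted subject changes an incidence by 100/n points: 100 for n = 1, 50 for n = 2, 25 for n = 4, and 3.7 for all 27. Subjects count once per system organ class or preferred term, so the shift occurs only if that subject has no other qualifying event in the row.

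**The case against.** The strongest reply is that the harm depends on one reading of an undefined phrase. Neither document speaks of the last attended visit. The phrase appears throughout as a general end of reporting and could mean the end of participation, in which case there is no gap. The date rules point the same way: they have no upper limit, and an event with no dates at all is assumed treatment-emergent. This is fair as to intent. But Protocol 10.2 uses both phrases in one section without equating them, and a programmer applying SAP 8.1.1 to a fully dated event has only the last-visit limit.

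Three stronger conclusions are tempting, and the documents do not support them.
- **That exit-causing events in general are lost.** They count whenever the Early Termination visit takes place. For a subject who is truly lost, a later event is unknown, and no change of window recovers it.
- **That signals found under Protocol 12.1 would be collected but not counted.** That follow-up is optional, and it is unclear whether it belongs to study participation at all. If it does, its remote contacts might count as visits: Appendix 1 already treats some remotely conducted contacts as study visits.
- **That the most serious events would vanish from the report.** They would appear in Listings 16.2.7.1 and 16.2.7.2, and a death would appear in disposition. SAP 8.1.1 also says that all AEs are summarised by maximum severity, though shell 14.3.1.2 is titled for TEAEs. The safety monitoring committee's triggers in Protocol 11.5 and 12.3 do not depend on TEAE status, so oversight during the trial is unaffected.

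**Conclusion.** The point stands in a narrow form. As written, the rule gives a wrong count for a fully dated event that starts after the last visit, in a subject who dies or leaves without an Early Termination visit and whose event is nevertheless reported. The error reaches the primary-endpoint tables and can make disposition and Table 14.3.3.3 disagree.

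This rests on reading the last study visit as the last visit that took place, the natural reading when a subject dies between visits. If the sponsor means the end of participation, the remedy is to say so. No expected number of omitted events can be given, because the documents supply no rates of death or early exit. With planned cohorts of one or two subjects, a single omission would be conspicuous, but the analyses are descriptive and the listings remain complete for whatever is recorded. The definition should be settled before the tables are run; it does not threaten the study's validity.

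**What to change.** In SAP 8.1.1, end the TEAE window at the subject's last day of study participation, defined as the latest of the last visit, the last recorded contact in this study, or death. State whether calls and laboratory tests arranged under Protocol 12.1 count as such contacts, and apply the same upper limit to partial dates. Enter the change in SAP section 11, which currently records only the dropped ERT-dose summary.

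At the next protocol amendment, reconcile the end dates in Protocol 10.2, 10.4 and 10.6.

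The SAP change is small and definitional, and it is enough to correct the tables for events already recorded. The protocol change costs more: Protocol 14.3 requires written ethics approval before an amendment takes effect, and moving the end date in 10.4 slightly lengthens the SAE reporting period for some subjects.

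### SAP 8.1.1 classifies an adverse event with a partial pre-infusion onset and a post-infusion end date as both treatment-emergent and not, with no order of precedence

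*SAP*

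**What the plan says.** Protocol 13.4 states: "The primary endpoint of this study is the incidence of treatment-emergent AEs (including SAEs"). SAP 3.2.1 repeats it. Both documents define treatment emergence by onset alone. SAP 8.1.1 has "any adverse event with an onset date on or after the date of the SB-318 infusion through the last study visit", and Protocol 10.2 has "any AE with an onset from any time from administration of the study treatment through the last study visit".

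SAP 8.1.1 then adds one rule for events with both dates missing and five unnumbered bullets for partially missing dates. Taken in order:

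- **Bullet 1** opens "If the onset date is missing and the non-missing end date is prior to the infusion date"; the event is not treatment-emergent.
- **Bullet 2** covers a partial end date that falls before infusion; not treatment-emergent.
- **Bullet 3** opens "If the end date is after the infusion date or the partial end date can be assumed to be on or after" infusion, and concludes "based on month and/or year), then the AE is assumed to be treatment emergent".
- **Bullet 4** opens "If the onset date is partial and can be assumed to be prior to the infusion date (based on the month and/or year") and continues "or the non-missing end date is prior to the infusion date then the AE is not considered treatment emergent".
- **Bullet 5** covers a partial onset taken to be on or after infusion; treatment-emergent.

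Only bullet 1 requires the onset date to be missing. No sequence or precedence is stated. SAP Section 4 allows no other imputation unless specified, so these bullets are the whole rule.

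**The concern.** Bullet 3 tests the end date and places no condition on onset. Bullet 4 tests the onset date and, in its first limb, places no condition on the end date. One event can satisfy both and receive opposite answers. Code that stops at the first match would follow bullet 3; code in which later rules overwrite earlier ones would follow bullet 4.

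The flag feeds the primary endpoint and every treatment-emergent table listed in SAP 8.1.1, including those for severity, relationship and seriousness. The date pattern is plausible. Adverse events are collected from consent (Protocol 10.2), screening may last about 3 months (Protocol 6.1), and Baseline procedures include liver biopsy, lumbar puncture and the start of prednisone (Protocol 6.3). The SAP shells provide for dates known only to the month or year.

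**Working it through.** **One example.** Infusion 15 June, onset recorded as May, end date 1 July.

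| Rule | Test | Result |
|---|---|---|
| General definition, SAP 8.1.1 and Protocol 10.2 | onset before infusion | not treatment-emergent |
| Bullet 3 | end date after infusion | treatment-emergent |
| Bullet 4 | partial onset before infusion | not treatment-emergent |

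**All date patterns.** The both-missing rule and the five bullets were applied literally to four kinds of onset (missing; partial before, in, or after the infusion month) and seven kinds of end date (missing; partial before, in, or after the infusion month; full before, on, or after the infusion day). Pairs with a post-infusion onset and a pre-infusion end were left out as impossible. So were complete onset dates, which the general definition decides directly. A date in the infusion month was not, by itself, counted as before or after infusion.

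- Read literally, two patterns conflict: partial onset before infusion with a full end date after it, and the same onset with a partial end date after it. Both pit bullet 3 against bullet 4.
- Read literally, five patterns match no rule. Three have an onset in the infusion month, with the end date missing, partial in that month, or full on the infusion day. Two have a missing onset, with the end date partial in the infusion month or full on the infusion day.
- With bullets 2 and 3 limited to a missing onset, no pattern conflicts, but the unmatched patterns rise from five to eight. Bullets 2 and 3 then no longer settle infusion-month onsets through the end date.

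**Size.** The plan states no figure for this. If the disputed event is a subject's only event in a row, the row moves by 100 × 1/n percentage points. The cohort plan (Protocol synopsis, Sample Size) gives one subject in one cohort and two in each of six others: 1 + 2×6 = 13. Two additional subjects in each of seven cohorts give 13 + 2×7 = 27, which reproduces the stated maximum.

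| n | Shift (points) |
|---|---|
| 1 | 100/1 = 100 |
| 2 | 100/2 = 50 |
| 13 | 100/13 = 7.7 |
| 27 | 100/27 = 3.7 |

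The shells show columns for only the two lower doses plus a total. If those columns hold the planned 1 + 2 = 3 subjects, which is an assumption, the shift in the total is 100/3 = 33.3 points.

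**The case against.** The best defence is that the bullets form two blocks: bullets 1 to 3 for a missing onset, bullets 4 and 5 for a partial one. Bullet 4's restatement of an end-date condition makes sense on that reading. It removes both conflicts and agrees with the general definition, which already points to not treatment-emergent in the example. It is a plausible reading, but the SAP does not state it, and a programmer working from the text need not adopt it. It also leaves more infusion-month onsets unmatched.

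A second defence concerns those onsets. A reader might infer that the SAP has no rule for them. That goes too far. As written, bullet 3 settles those with an end date clearly after infusion, and bullet 4 those with a full end date before it. Bullet 5 arguably covers the infusion month too, since a month-only date can be taken as on the infusion date only if that month counts. But if bullet 5 does apply, it opposes bullet 4 when the full end date precedes infusion, so an explicit rule is still needed.

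A third defence is that little harm could follow. The study is descriptive with no hypothesis testing, and the listings show every event with its observed dates and a treatment-emergent flag. A disputed classification could therefore be seen and checked. This limits the consequence but does not remove the contradiction.

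**Conclusion.** The contradiction stands in the SAP text for two date patterns, and bullet 3's result in them is contrary to the onset-based definition in both documents. The shifts of 100, 50, 7.7 and 3.7 points are conditional: such an event must occur, and it must be the subject's only event in that row. Overall incidence of any treatment-emergent event changes only if the subject has no other one; rows by system organ class or preferred term are more exposed.

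A reader might infer that the primary endpoint as a whole turns on the order in which the bullets are programmed, because events that start before infusion and end after it are likely. The documents do not support that. They show no event with the required partial dates. Events with complete onset dates are decided by the general definition. Adverse events are queried at each visit (Protocol 10.2), which should limit partial dates. This is a localised error in a rule, worth correcting because the cohorts are very small and the correction is cheap.

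**What to change.** 1. In bullets 2 and 3, add the condition that the onset date is missing. Partial onsets are then classified by month and year under bullets 4 and 5.
2. In bullet 3, make the full end-date condition on or after infusion, so that a missing onset with an end date on the infusion day is classified.
3. State that a partial onset in the infusion month, or in the infusion year if only the year is known, is treatment-emergent unless the full or partial end date is before infusion.

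One pattern would still rest on interpretation: a missing onset with a partial end date in the infusion month. A clause saying whether bullet 3 counts that month as on or after infusion would close it.

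The cost is a few lines of SAP text and the matching lines of the derivation program. No data collection changes. It should be settled before the flag is derived.
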